**The Effect of Etelcalcetide on Bone-tissue Properties and Calcification
Propensity in End Stage Kidney Disease**

Principal Investigator: [name], MS

AAAR6244

NCT03960437

Protocol Version January 3, 2020

Title: The effect of etelcalcetide on bone-tissue properties and calcification propensity in end stage kidney disease

Hypotheses: Our hypothesis is that etelcalcetide treatment improves bone tissue-properties and bone mineral density by reducing remodeling. We also hypothesize that etelcalcetide's ability to lower serum calcium will decrease propensity of serum to calcify as determined by T50.

[figure not shown]
Background and Study Objectives

Chronic kidney disease – mineral and bone disease (CKD-MBD) is a systemic disorder of bone and mineral metabolism in patients with CKD. As kidney function declines, abnormal vitamin D metabolism and renal phosphate handling drive the development of hyperparathyroidism (HPT), hyperphosphatemia, renal osteodystrophy and soft tissue calcifications. Clinical outcomes associated with CKD-MBD include bone fractures, cardiovascular events and death. Treatment of CKD-MBD is centered around the suppression of parathyroid hormone (PTH) by supplementation with vitamin D (parent and active D) and correction of hyperphosphatemia. In patients with end stage kidney disease (ESKD), target levels of PTH recommended by the Kidney Disease Improving Global Outcomes (KDIGO) guidelines are in the range of 2-9 times the upper limit of normal (ULN) for the PTH assay¹. However, in patients with long-standing ESKD, abnormalities may develop in the parathyroid gland that both diminish responsiveness to treatment and lead to failure to achieve PTH levels within the KDIGO target range. PTH levels greater than the target range increase the risks of bone loss, fractures, soft tissue calcification and cardiovascular events. In these cases, treatment with a calcimimetic, a pharmacologic agent that enhances sensitivity of the parathyroid gland to serum levels of calcium, can restore PTH levels to goal. Etelcalcetide is a Food and Drug Administration (FDA) approved calcimimetic for the treatment of secondary HPT in adult patients with CKD on hemodialysis²⁻⁴. The proposed prospective cohort study will investigate the effects of etelcalcetide on the bone and vascular calcification components of CKD-MBD. We will test if treatment with etelcalcetide improves bone properties on the tissue level, increases areal bone mineral density (BMD) by dual energy X-ray absorptiometry (DXA), improves cortical and trabecular BMD and microarchitecture and mechanical competence by high resolution peripheral computed tomography (HR-pQCT), and decreases serum propensity to calcify soft tissues. For all Aims, the enrollment scheme and study timeline are described in Figures 1 and 2, respectively.

Hypothesis 1. Etelcalcetide improves bone-tissue properties in patients with ESKD and severe hyperparathyroidism.

Aim 1. To test if 6-months of treatment

Figure 1. Study Procedures for All Aims

with etelcalcetide improves bone hardness and mineralization using Ramen/nanoindentation and remodeling by histomorphometry using the quadruple label transiliac crest bone biopsy method in 20 ESKD patients with severe HPT.

Figure 2. Study timeline.

[figure not shown]

Table 1: Data Collection at each Study Visit

	Baseline	3 Months	9 Months
Informed consent	x		
Medical History	x		x
Physical Exam	x		x
Kt/V	x	x	x
Biomarkers of bone formation and resorption (BSAP, P1NP, CTX)	x	x	x

Procedures. This is a single-arm prospective cohort study to test the effects of 6-months of treatment with etelcalcetide on bone-tissue properties. We will obtain a single quadruple label bone biopsy to assess longitudinally the effects of 6-months of treatment with etelcalcetide on bone properties at the tissue level.

We will enroll 20 adult patients with ESKD on hemodialysis who are scheduled to receive etelcalcetide for the treatment of HPT per standard of care. These 20 patients with ESKD will be treated with etelcalcetide to maintain levels of PTH between 300 and 400 pg/mL, which is at the mid-range of the KDIGO recommended range (2-9 times the ULN for the PTH assay¹) for 6 months. Patients will be identified for inclusion based on clinical need for the treatment of severe HPT and high turnover bone disease and only patients whose treating physician plans to initiate etelcalcetide will be included. HPT will be defined by the KDIGO guidelines (PTH >9-times the ULN for the PTH assay¹) and high turnover bone disease will be defined by a total alkaline phosphatase level \geq upper tertile of the reference range for the assay. At study start, patients will undergo the initial double labeling procedure with tetracycline (TCN; 3-days of TCN followed by 12-days off TCN followed by 3-days of TCN); during the labeling period etelcalcetide will not be administered (**Figure 2**). Patients will then undergo a 3-month etelcalcetide dose-titration phase to ensure that PTH levels are consistently maintained within target range (300-400 pg/mL), followed by a 6-month treatment (maintenance) phase. At the study endpoint (6-months of treatment), the final set of labels for transiliac crest bone biopsy will be given (3-days of demeclocycline followed by 12-days off demeclocycline followed by 3-days of demeclocycline) and bone biopsy will occur 5-days after the last dose of demeclocycline. During the final labeling period, the dose of etelcalcetide will continue to target the goal PTH level and the patient will continue to be managed as clinically indicated. The quadruple label approach permits longitudinal assessment of both dynamic indices of histomorphometry and bone-tissue level properties pre- and post-intervention, with the use of a single biopsy. The first label (TCN) is given prior to the initiation of etelcalcetide and the second label (demeclocycline) is given after 6-months of treatment (maintenance) with etelcalcetide. The fluorescence of tetracycline and demeclocycline differs, permitting differentiation of the labels under fluorescence microscopy and determination of dynamic indices of histomorphometry pre- and post-intervention. To assess bone tissue level effects of treatment, we will use a Raman/Nanoindentation system. This system allows the differentiation of tetracycline (pre-treatment) and demeclocycline (post-treatment) labels and permits precise measurement of localized bone tissue properties (e.g., mineral/matrix, collagen) and indentation properties (e.g., hardness) within these regions. Additionally, we will use 3-dimensional micro-CT (μ CT) imaging (resolution 3 μm^3) to obtain more complete structural indices from the bone biopsy specimens at the 6-month time point. Patients will have blood collected and stored at -80°C, at baseline (pre-treatment) and after 3- and 6-months of treatment (i.e., maintenance phase) (**Table 1**). Blood will be assayed for calcium, phosphorus, PTH, vitamin D metabolites, bone formation (bone specific alkaline phosphatase [BSAP], procollagen type-1 N-terminal propeptide [P1NP]) and resorption (C-Telopeptide [CTX]) markers, FGF-23 and sclerostin.

Bone biopsy with quantitative histomorphometry and nanoindentation/Raman spectroscopy. After bone biopsy, the specimens will be transferred to [name] laboratory for tissue analysis (described below).

μ CT. 3D trabecular and cortical structure will be assessed on biopsies before embedding using a Skyscan 1172 system (scanning resolution of 6 μm^3). Outcome measurements will include both cortical parameters (porosity [%], mineralization [average value and variation] and thickness) and trabecular parameters (BV/TV, trabecular number, separation, thickness, and connectivity density) using manufacturer software and standard analytical protocols. At study initiation, we will perform short-term precision measurements on selected structural and mechanical properties. QC procedures are enforced by the in-house software system, and include weekly scanning of a QA/ μ CT phantom. The software system's QA analysis monitors scanner performance and normalizes results for any fluctuations. QA data and specimen results can be exported to SAS or Excel.

Quantitative histomorphometry. Following CT scans, specimens will be embedded in methyl methacrylate using standard protocols. Sections will be cut with a rotary microtome and either left unstained or stained with McNeal tetracrome or tartrate resistant acid phosphatase for analysis. Histomorphometric indices will be defined in accordance with the American Society for Bone and Mineral Research⁵. The following histomorphometric indices will be measured or calculated: osteoid surface, area, and width; osteoclast surface, eroded surface, resorption depth, resorption period; cancellous wall width, mineral apposition rate, bone formation rate, adjusted

PTH, Vitamin D metabolites, Serum calcium and phosphorus, FGF-23, Sclerostin, T50	x	x	x
Bone biopsy Labeling (for participants enrolled in Aim 1)	x		x
Bone biopsy (for participants enrolled in Aim 1)			x
Imaging: DXA and HR-pQCT	x		x
AGE Reader	x		x

apposition rate, mineralization lag time, activation frequency. Note: architectural properties (BV/TV, porosity, etc) will not be collected, as these will be obtained from CT as above.

Bone-tissue properties. We will use an integrated Raman/Nanoindentation system, which permits precise measurement of localized bone tissue properties (e.g., mineral/matrix, collagen) and indentation properties (e.g., hardness) within identical regions. Areas within the TCN and demeclocycline double label will be assessed for nanoindentation properties, and subsequently the same spatial location will be assessed for Raman-based measurements. Nanoindentation will occur using a Berkovich diamond indenter loading to a peak load of 10mN, a strain rate of 0.05 seconds and a holding period of 10 seconds. Oliver and Pharr methods will be used to determine the stiffness and hardness of the unloading curves. A total of 12-15 indentations will be performed within a given region. Following indentation, the same spatial regions will be assessed with Raman spectroscopy to determine the phosphate and matrix peaks after background and baseline shift correction. The ratio of phosphate:mineral will be calculated, along with other parameters (crystallinity and collagen crosslinking).

Hypothesis 2. Etelcalcetide will improve bone density, microarchitecture, and biomechanical competence in patients with ESKD.

Aim 2. To test if 6-months of treatment with etelcalcetide improves femoral neck areal BMD measured by DXA and failure load at the ultradistal radius measured by application of finite element analysis to HR-pQCT datasets. We will also quantify the effect of 6-months treatment with etelcalcetide on changes in areal BMD at the spine, total hip, and one-third and ultradistal radius measured by DXA, and cortical and trabecular volumetric BMD and microarchitecture, cortical porosity and tissue mineral density, and biomechanical competence at the ultradistal radius and tibia measured by HR-pQCT with application of finite element analysis.

Procedures. We will enroll 35 patients (20 from Aim 1 and 15 *de novo*) into this prospective single-arm cohort study to test the hypothesis that 6 months of treatment (maintenance) with etelcalcetide will improve bone density, microarchitecture and mechanical competence measured by DXA and HR-pQCT with application of finite element analysis (FEA). Similar to **Aim 1**, eligibility for enrollment into **Aim 2** will be based on a PTH level >9 -times the ULN for the PTH assay (**Figure 1**), as well as their treating physician's plan to initiate etelcalcetide per standard of care. However, the presence of high turnover bone disease based on total alkaline phosphatase will not be a criterion for enrollment into **Aim 2**. Furthermore, all patients enrolled in **Aim 1** will be automatically enrolled into **Aim 2** unless they choose to opt-out of **Aim 2**. As per **Aim 1** (**Figure 2**), after enrollment, patients will undergo a 3-month dose titration phase to ensure that PTH levels are stability maintained within the target range (300-400 pg/mL), followed by a 6-month treatment (maintenance) phase. All patients will have imaging (DXA and HR-pQCT) performed at baseline (prior to drug) and after 6-months of maintenance treatment.

Imaging Methods for Measurement of Bone Mass, Microarchitecture, and Mechanical Competence

- **DXA.** areal BMD of spine (L1-4, AP), right proximal femur, forearm and whole body using Hologic QDR 4500 (Hologic, Inc., Waltham, MA) in the array (fan beam) mode. Phantoms are scanned daily for QA. Short term, *in vivo* precision is 0.68%, 1.36%, and 0.70% for spine, FN, and radius respectively.
- **HR-pQCT of the ultradistal radius and tibia.** XtremeCT2 (Scanco Medical AG, Brüttisellen, Switzerland, voxel size 60 μ m). Methods and QC are described in our publications^{6, 7}. Precision: cortical and volumetric trabecular BMD=0.9% \pm 7.1% and 2.3 \pm 3.5%, respectively. HR-pQCT of the forearm will be performed at the non-dominant forearm. If dialysis access is located at the non-dominant forearm, we will use the dominant forearm for HR-pQCT imaging.

Mechanical Analysis of Skeletal Imaging. [name] MS will perform analyses of HR-pQCT datasets.

HR-pQCT Finite Element Analysis (FEA). [name] will estimate mechanical competence (strength) from HR-pQCT images. Each image is converted to a μ FE model by directly converting bone voxels to 8-node elastic brick elements. A uniaxial displacement equaling 1% of the bone segment height is applied perpendicularly to the distal surface of the radius or tibia while the proximal surface is imposed with zero displacement along the same direction. The total reaction force is calculated from the linear μ FE analysis, and the axial stiffness is calculated as the reaction force divided by the imposed displacement.

HR-pQCT Cortical Porosity. [name] will conduct analyses of cortical porosity using methods that have been described and validated in recent publications⁸.

Hypothesis 3. Etelcalcetide decreases serum calcification propensity in patients with ESKD.

Aim 3. To test if 6-months of treatment with etelcalcetide decreases serum propensity to calcify soft tissues. In a single-arm study of 35 patients with ESKD treated with 6-months of etelcalcetide, we will measure T50, calcitropic hormones, serum calcium and phosphorus, bone turnover markers, FGF-23 and Sclerostin pre-treatment and 3- and 6-months after treatment.

Procedures. We will enroll 35 patients (20 from Aim 1 and 15 *de novo*) into this prospective single-arm cohort study to test the hypothesis that 6 months of treatment (maintenance) with etelcalcetide will decrease the propensity to calcify soft tissues as measured by T50. Similar to **Aim 1**, eligibility for enrollment into **Aim 3** will be based on a PTH level >9-times the ULN for the PTH assay (**Figure 1**), as well as their treating physician's plan to initiate etelcalcetide per standard of care. However, the presence of high turnover bone disease based on total alkaline phosphatase will not be a criterion for enrollment into **Aim 3**. Furthermore, all patients enrolled in **Aim 1** will be automatically enrolled into **Aim 3** unless they choose to opt-out of **Aim 3**. Thus, we will use the biochemical data from the 20 enrollees participating in **Aim 1** and enroll an additional 15 patients to be treated with etelcalcetide. As per **Aim 1** (**Figure 2**), after enrollment, patients will undergo a 3-month dose titration phase to ensure that PTH levels are stability maintained within the target range (300-400 pg/mL), followed by a 6-month treatment (maintenance) phase. Patients will have blood collected and stored at -80°C, at baseline (pre-treatment) and after 3- and 6-months of treatment (i.e., maintenance phase). Blood will be assayed for T50, calcium, phosphorus, PTH, vitamin D metabolites, bone formation (BSAP, P1NP) and resorption (CTX) markers, FGF-23 and sclerostin. We will assess the effect of treatment on changes in levels of T50, a clinically relevant biomarker of calcification propensity^{9, 10}. We will also determine relationships between changes in T50 and changes in phosphorus, calcium, bone turnover markers and calcitropic hormones.

Exploratory. None

Primary and Secondary Endpoints for Each Aim

Aim 1

1. Primary Endpoints: Hardness
2. Secondary Endpoints: Bone formation rate, mineralization density

Aim 2

1. Primary Endpoints: Changes in: (a) femoral neck areal BMD by DXA and (b) radius failure load by HR-pQCT
2. Secondary Endpoints: Changes in: (a) spine, total hip, and one-third and ultradistal radius BMD by DXA and (b) radius and tibia cortical density, thickness, porosity and tissue mineral density, and trabecular density, thickness, number and spacing

Aim 3

1. Primary Endpoint: Change in T50 (percent and absolute)
2. Secondary Endpoints: Changes in PTH, calcitropic hormones, FGF-23, Sclerostin, calcium and phosphorus

Statistical methods (for analysis of primary and secondary endpoints or primary/interim analysis)

For All Aims, distributions will be examined and Anderson-Darling tests of normality and Q-Q plots will be used to guide the application of transformations to normalize the values prior to inferential testing. (Data analyzed from transformations will be reported in raw units). Inferential tests will be adjusted for multiple comparisons within a measurement domain (BMD within DXA, cortical, trabecular and FEA within HRpQCT, and each of the four compartments within histomorphometry) using a resampling, step-down procedure to control the family-wise error rate. We favor this over a false-discovery rate approach given the limited number of hypotheses within each measurement domain and that the measurement domains are traditionally seen as free to vary independently of each other^{11, 12}.

For Aim 1. A two-tailed dependent T-test of the change in hardness measured by Ramen nano-indentation and mineralization measured by histomorphometry obtained primary dynamic and secondary structural bone quality

outcome values from the pre-treatment baseline to the 6-month endpoint will be reported with an alpha-level of 5% as the criterion for statistical significance. Outcome data missing, for whatever reason, will not be imputed.

For Aim 2. A two-tailed dependent T-test of the change in femoral neck BMD by DXA and failure load measured at the distal radius by HR-pQCT from pre-treatment to the 6-month endpoint will be reported with an alpha-level of 5% as the criterion for statistical significance. Secondary endpoints include treatment differences in change in cortical density, thickness and porosity, trabecular density and thickness and spacing, and areal BMD at the forearm, spine, and total hip. Other predictors to be tested in multiple regression models of change from baseline include demographic characteristics collected in **Aim 1** and PTH, calcitropic hormones, bone formation and resorption markers, sclerostin, and FGF-23 collected in **Aim 3**. A final multiple regression model will be based on predictors that are significant in multiple regression models including baseline bone measure.

For Aim 3. A two-tailed dependent T-test of the change in primary calcification propensity (T50) and secondary biochemical indices (calcitropic hormones, FGF-23, sclerostin, calcium and phosphorus) from pre-treatment baseline to the 6-month endpoint will be reported with an alpha-level of 5% as the criterion for statistical significance. Secondary exploratory analyses will assess the within-subject temporal course of change in the biochemical outcome with linear mixed models for repeated measures with time as a fixed effect (0, 3 and 6 months); the baseline value of the dependent variable entered as a continuous covariate; and a covariance structure determined by empirical testing performed prior to inferential testing. We will also assess whether the **Aim 1** participants differ from the patients recruited *de novo* for **Aim 3** with an independent T-test both of the two groups' baseline values and of the two groups' change in values from baseline to the 6-month endpoint. We will explore the covariances between changes in T50 and other biochemical markers of bone turnover and calcitropic hormones with simple and multiple regression with synchronized and lagged observations in time to determine whether leading, cotemporaneous or following patterns exist among these measures.

Subject Recruitment and Selection

Study site and number of patients eligible for enrollment. ESKD patients receiving hemodialysis at the Rogosin Institute, meeting enrollment criteria, and whose treating physicians intend to initiate treatment with etelcalcetide will be asked to participate in this study. Rogosin is the largest provider of hemodialysis in New York City and provides hemodialysis services to over 1300 patients. Approximately 25% of patients at Rogosin have PTH levels > 9-times the ULN for the PTH assay. Therefore, there are adequate numbers of patients at Rogosin who may be able and willing to participate in this prospective cohort study.

Enrollment Criteria

Inclusion criteria

For All Aims:

1. Patient has provided informed consent.
2. Patient is 18 years of age or older.
3. Patient must be receiving maintenance hemodialysis for at least 3 months, with adequate hemodialysis with a delivered Kt/V 1.2 or urea reduction ratio (URR) 65% within 4 weeks prior to screening laboratory assessments.
4. Dialysate calcium concentration must be stable for at least 4 weeks prior to screening laboratory assessments.
5. Patient must have severe HPT as defined by two laboratory screening pre-dialysis serum PTH values >9-times ULN for the PTH assay, measured on two consecutive monthly lab checks prior to entering the study.
6. The patient has an uncontrolled PTH defined by KDIGO as a PTH greater than 9 times the upper limit of normal of the assay (720 pg/mL for Rogosin):

AND one of the following:

- The patient has never been on cinacalcet OR,
- The patient received daily cinacalcet for less than 3 months and has been off cinacalcet for at least 3 months prior to enrollment OR ,

- The patient received daily cinacalcet for more than 3 months and has been off cinacalcet for at least 6 months prior to enrollment OR,
- The patient received a modified dose of three times weekly cinacalcet and has been off cinacalcet for at least one month prior to enrollment.

7. Scheduled to receive etelcalcetide for the treatment of HPT per standard of care.
8. If receiving vitamin D sterols, patient must have had no more than a maximum dose change of 50% within the 4 weeks prior to screening laboratory assessments, remain stable through randomization, and be expected to maintain stable doses for the duration of the study, except for adjustments allowed per protocol*.
9. Patient must have one screening pre-dialysis serum Ca laboratory value at least at the lower limit of normal for the assay measured within 4 weeks prior to entering the study.
10. A patient receiving calcium supplements must have had no more than a maximum dose change of 50% within 2 weeks prior to screening laboratory assessments and remain stable throughout the study, except for adjustments allowed per protocol*.
11. A patient receiving phosphate binders must have had no more than a maximum dose change of 50% within the 2 weeks prior to screening laboratory assessments, remain stable through, and be expected to maintain stable dose for the duration of the study, except for adjustments allowed per protocol*.
12. The treating physician considers the etelcalcetide dose and timing points described in this protocol as acceptable/optimal for their patient.
13. Female patients must be willing to use highly effective contraception during the study and for 3 months after the last dose of etelcalcetide (unless postmenopausal or surgically sterilized).

For Aim 1:

1. Total alkaline phosphatase \geq the upper tertile of the reference range for the assay

Exclusion criteria

For All Aims:

1. Currently receiving treatment in an investigational device or drug study, or less than 30 days since ending treatment on an investigational device or drug study(s).
2. Currently receiving investigational procedures while participating in this study.
3. Patient with controlled PTH as defined by KDIGO as a PTH of 2 to 9 times the upper limit of normal of the assay.
4. Patients has received a bisphosphonate, denosumab or teriparatide during the 12 months prior to screening.
5. Anticipated or scheduled parathyroidectomy during the study period.
6. Patient has received a parathyroidectomy within 6 months prior to dosing.
7. Scheduled kidney transplant during the study period or anticipated living donor evaluation within three months of recruitment
8. Patient has an unstable medical condition based on medical history, physical examination, and routine laboratory tests, or is otherwise unstable in the judgment of the Investigator.
9. Bilateral lower extremity amputations or non-ambulatory
10. Metabolic bone diseases not related to the kidney (i.e., Pagets, Osteogenesis Imprefecta)
11. Untreated hyperthyroidism or hypoparathyroidism
12. Malignancy within the last 5 years (except non-melanoma skin cancers or cervical carcinoma in situ).
13. Patient is pregnant or nursing.
14. Patient likely to not be available to complete all protocol-required study visits or procedures, and/or to comply with all required study procedures to the best of the patient and Investigator's knowledge.
15. Weight >300 pounds

For Aim 1:

1. Allergy to tetracycline or demeclocycline.

Early Study Cessation Clause

For patients who may get a kidney transplant during the study: If patients have been on etelcalcetide for at least 3 months, end of study procedures (bone biopsy, bone imaging, and labs) will be performed and patients will be included in the final analysis as long as patients come in within 4 weeks after transplant.

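### Loss of tetracycline label before the single biopsy biases the paired change in bone formation rate toward no fall, and the plan makes no allowance for it

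*Combined protocol and SAP*

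**What the plan says.** The Hypotheses paragraph expects etelcalcetide to act by lowering remodeling. Aim 1, Procedures, selects patients on "clinical need for the treatment of severe HPT and high turnover bone disease", with turnover judged by total alkaline phosphatase.

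There is one biopsy. Table 1 places it at the last visit only. Tetracycline is given before the drug and demeclocycline after the maintenance phase. Because the two fluoresce differently, the plan describes the method as "permitting differentiation of the labels under fluorescence microscopy and determination of dynamic indices of histomorphometry pre- and post-intervention".

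The Aim 1 endpoint list reads "Secondary Endpoints: Bone formation rate, mineralization density". The paragraph on quantitative histomorphometry lists "cancellous wall width, mineral apposition rate, bone formation rate, adjusted" apposition rate and, further on, activation frequency.

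Statistical methods, Aim 1, applies a two-sided paired t-test at 5% to changes between baseline and the 6-month endpoint, and leaves missing outcomes unimputed. That sentence is hard to parse and does not name bone formation rate, but it does cover dynamic bone outcomes.

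The plan does not mention loss of tetracycline label to resorption, a correction for it, a minimum labeled surface or a sensitivity analysis. The nearest statement, in Sample Size Justification for Aim 1, cites turnover figures from a cinacalcet biopsy study to argue that hardness can be measured. That concerns whether some labeled bone can be found, not what share of the original label is left.

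**The concern.** Bone formation rate is the apposition rate multiplied by the share of bone surface that carries label. The paired test treats the pre- and post-treatment values as equally complete, but one label set has been exposed to resorption for about nine months longer than the other. Two label colors solve the problem of telling the sets apart. They do not solve survival.

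The patients are chosen because their bone is being turned over quickly, and bone formation rate is the listed endpoint closest to the proposed mechanism. If the baseline is undercounted, a real fall in remodeling is shrunk, and a null result could be misread as evidence that remodeling did not fall. Activation frequency, which is derived from bone formation rate, inherits the problem.

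**Working it through.** **Plan's own figure.** None exists for bone formation rate. The only Aim 1 calculation is the 0.91 SD detectable change in hardness. It does not reproduce as a paired test: n = 20, two-sided 5% and 80% power give 0.66 SD, while a two-group formula with 20 per group gives 0.909 SD. That is a separate matter and does not enter below.

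**Label age at biopsy** (Aim 1, Procedures; 30.44 days per month assumed)
- First labels: "3-days of TCN followed by 12-days off TCN followed by 3-days of TCN", so 3 + 12 + 3 = 18 days.
- "Patients will then undergo a 3-month etelcalcetide dose-titration phase", "followed by a 6-month treatment (maintenance) phase": 9 × 30.44 = 274 days.
- Final labels: "3-days of demeclocycline followed by 12-days off demeclocycline followed by 3-days of demeclocycline", so 18 days, then 5 days to biopsy.
- Tetracycline: last dose 274 + 18 + 5 = 297 days old; first dose 297 + 18 = 315 days old.
- Demeclocycline: 5 days (last dose) to 18 + 5 = 23 days (first dose).

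**Effect on the paired change.** Let s be the share of tetracycline label surviving to biopsy and f the true fractional fall. Take the demeclocycline label as intact and, for now, the bone surface as unchanged. Observed baseline = s × true baseline, so

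apparent change = (1 - f)/s - 1.

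This is zero at s = 1 - f and positive only for s below that, which is the true post/pre ratio. Neither s nor f is in the documents; both are assumed here.

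| True change | s = 0.9 | s = 0.7 | s = 0.6 | s = 0.5 | s = 0.3 |
|---|---|---|---|---|---|
| 0% | +11% | +43% | +67% | +100% | +233% |
| -20% | -11% | +14% | +33% | +60% | +167% |
| -40% | -33% | -14% | 0% | +20% | +100% |
| -50% | -44% | -29% | -17% | 0% | +67% |
| -70% | -67% | -57% | -50% | -40% | 0% |

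**Rough plausibility of s.** Take the 13.1 eroded perimeter quoted in Sample Size Justification for Aim 1 (read as a percentage), assume an eroded site lasts P = 30 to 120 days, and assume resorption falls at random. Then s = exp(-0.131 × 297/P).
- Unchanged turnover: exp(-1.30) = 0.27 at P = 30; exp(-0.32) = 0.72 at P = 120.
- Resorption halved throughout: 0.52 to 0.85. A true 50% fall would then appear as 0.5/0.52 - 1 = -4% to 0.5/0.85 - 1 = -41%.

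These figures rest on assumed site life and on another study's patients. They show that material loss is plausible, not how large it is.

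**Effect on power.** Take the baseline of 799 from the same cited study, a true 50% fall, and an SD of change of 334 (assumed; it is the cited baseline SD). The standardized difference is (s × 799 - 399.5)/334: 1.20 at s = 1, 0.72 at s = 0.8 and 0.24 at s = 0.6. Power of the paired test at n = 20 is over 99%, 86% and 17% respectively.

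**Referent surface.** The surface present at first labeling cannot be seen at biopsy. If c is the surface at biopsy divided by the surface at first labeling, the formula becomes (1 - f) × c/s - 1. For f = 0.4 and s = 0.9: c = 0.9 gives -40% (the errors cancel), c = 1.1 gives -27%, and c = 0.8 gives -47%. The documents do not fix the direction of c.

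**The case against.** The strongest reply has four parts.

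- **Treatment protects the label.** The drug starts after the tetracycline labels, so nearly all the loss occurs on treatment. If turnover falls, less label is lost, and s and f cannot be chosen independently. This stands, and it makes the low-s cells less likely for good responders. It also means that patients whose turnover stays high lose the most baseline label: a non-responder at s = 0.7 would show +43%. The Early Study Cessation Clause allows biopsy after as little as 3 months on drug, so label age varies between patients too. A single correction factor would not suffice.
- **Heavy loss is inferred.** The alkaline phosphatase threshold for Aim 1 sits inside the reference range, so it is a loose marker of high turnover. This stands as a limit on size. Entry also requires PTH above 9 times the upper limit of normal, which supports raised turnover.
- **The bias works against the hypothesis.** As far as label loss alone goes, an observed fall remains credible. This stands. The damage is to the reading of a small, null or positive change.
- **The single biopsy is deliberate.** Protection against risk says the method spares a second procedure. This stands, and the remedy should keep it.

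A reader might go further and infer that the fall will be reversed, that the measured baseline is a strict lower bound, or that the primary endpoint is compromised. The documents support none of these. Reversal needs s below the true post/pre ratio, and neither is known. The referent-surface error has no fixed sign, so only the labeled extent is bounded from below. Hardness is measured inside surviving label and does not depend on how much surface remains; selection of surviving sites is a different question.

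**Conclusion.** The point holds for bone formation rate and activation frequency. The schedule, the single late biopsy, the paired test and the absence of any allowance for label loss are all in the document. The direction of the label-loss component follows from the design: for any s below 1, baseline labeled surface is understated and the paired change is pushed toward no fall.

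The size is not derivable. The illustration for a true 40% fall (-33% to +20% for s from 0.9 to 0.5) rests on assumed survival, an intact demeclocycline label and an unchanged bone surface. Survival is likely to be higher where turnover falls on treatment. The consequence concerns a secondary endpoint, but one that bears directly on the claimed mechanism.

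**What to change.** Keep the single biopsy and keep bone formation rate as a secondary endpoint. In the Aim 1 statistical section:

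1. State that the paired t-tests of bone formation rate and activation frequency are not interpreted as unbiased changes, and that a null or positive change cannot be read as no reduction in remodeling.
2. Pre-specify a sensitivity table of the change over a wide assumed range of label survival, for example 0.3-1.0. Note that the change in bone surface adds an error of unknown sign, and do not describe the baseline as a lower bound.
3. Report the paired change in mineral apposition rate alongside. It is already on the list of indices and does not depend on labeled extent. It is supportive only: it comes from surviving sites and does not capture how much surface is active.
4. Pre-specify the changes in BSAP, P1NP and CTX as the cross-check for the turnover claim. Table 1 already schedules them at a true baseline, but the plan does not link them to the histomorphometry.

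The cost is wording, one table and a little more analysis, with no new visit, assay or procedure. The downside is a weaker stated conclusion for bone formation rate.
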